6.9.2 Secondary Endpoints

6.9.2.1 HbA1c/Responder Analysis

The number and percentage of subjects achieving HbA1c ≤6.5% will be summarized for each treatment group at each scheduled visit without LOCF, Week 30/LOCF_H, and Week 30/LOCF_{All}. Comparisons between treatment groups will be performed for responses at each visit, with Week 30/ LOCF_H being primary, based on a logistic regression model with treatment group and BMI strata as factors and baseline HbA1c as a covariate. Odds ratios,

95% CIs (Wald), and p-values will be presented. The same summary and analysis will be performed for HbA1c <7.0%.

6.9.2.2 Body Weight

The change from baseline and percent change from baseline in body weight at each scheduled visit will be analyzed using an MMRM for the mITT Population and repeated on the PP Population. The factors in the model will be HbA1c strata, BMI strata, treatment group, baseline value, visit, and the treatment group by visit interactions. An unstructured covariance matrix will be used (TYPE=UN). No imputation will be performed. The least-squares means for change from baseline at each visit will be estimated and compared between treatment groups.

As a supportive analysis, the change from baseline and percent change from baseline to Week 30/LOCF_{All} in body weight will be analyzed for the mITT Population using linear contrasts from an analysis of covariance (ANCOVA) model with treatment group, HbA1c strata (<8.5%, ≥8.5%), and BMI strata (<30, ≥30 kg/m²) as factors and the baseline body weight value as a covariate. The least-squares means, standard errors, and the 2-tailed 95% confidence intervals (CIs) for each treatment group and for comparison of OPK-88003 to placebo will be presented. The 2-sided p-values testing for significance within treatment group change from baseline and comparison between treatment groups will be presented.

The number and percentage of subjects achieving >5% weight loss will be summarized for each treatment group at each scheduled visit without LOCF and Week 30/LOCF_{All}. Comparisons between treatment groups will be performed for responses at Week 30 based on a logistic regression model with treatment group, HbA1c strata, and BMI strata as factors and baseline body weight as a covariate. Odds ratios, 95% CIs (Wald), and p-values will be presented.

6.9.2.3 Fasting Plasma Glucose

The same MMRM and ANCOVA model as for body weight above will be performed for the change from baseline in FPG. If Week 30 measurement is missing, the last valid post-baseline observation (LOCF) algorithm will be applied to impute the missing Week 30 value only for subjects that have early termed due to hyperglycemia (Week 30/LOCF_H).

CCI

CCI

CCI

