## **9 STUDY ACTIVITIES**

### **9.1 Screening/Visit 1 (Day -14 to Day -1)**

At this visit, the following study activities will be performed:

- Informed consent will be reviewed and the ICF signed prior to any study-related activities are performed
- Inclusion/exclusion criteria will be reviewed
- Medical history (including diabetes and medication history), demographics and health habits (alcohol, tobacco use) will be reviewed
- Physical examination will be performed, fasting weight and height will be measured
- Single 12-lead ECG will be obtained after at least 5 minutes of supine rest
- Vital signs will be assessed (supine blood pressure and pulse rate will be assessed following 12-lead ECG and prior to any blood draws)
- Blood samples will be collected:
  - Serum chemistry
  - Serum calcitonin
  - Hematology
  - Triglycerides

- Fasting glucose
- HbA1c
- Serology
- Serum pregnancy test/FSH (females, at the investigator's discretion)
- Urinalysis

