6 STATISTICAL METHODOLOGY

6.1 Sample Size Determination

Subjects will be randomized at an approximate ratio of 1.75:1 (OPK-88003:placebo). A sample size of 48 subjects in the active arm and 27 subjects in the placebo arm will provide at least 90% power to detect superior glycemetic control over placebo represented by -0.8% in HbA1c levels after 30 weeks of treatment. This assumes a common standard deviation (SD) of 1.0% and a two-sided alpha of 0.05. The assumptions are based on variability in previously obtained HbA1c results from the OPK-88003 phase 2 trial XNAA.

Approximately 110 subjects were enrolled in an effort to obtain 88 completed subjects (56 subjects completing in the active arm and 32 subjects completing in the placebo arm).

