6.2 Baseline, Endpoint, and Other Statistical Considerations

The clinical statistical efficacy and safety analyses will be performed by Medpace.

First dose of study drug refers to the first dose of blinded study drug (Week 0 Day 1).

Baseline will be the measurement at Week 0 Day 1. If missing, the last valid measurement prior to the first administration of study drug will be used as baseline.

Any measurements/events that occur after the subject started rescue therapy will not be included in the efficacy analyses.

Unless specified otherwise, treatment groups will be OPK-88003 and placebo for summaries and analyses. Additional explorations may be done by OPK-88003 dose.

Descriptive statistics (n, mean, standard deviation, median, minimum, and maximum) will be used to summarize the continuous efficacy and safety data by treatment group. The count and frequency will be used to tabulate categorical measurements.

Data will be used as it is reported. LOCF may be used when specified. The value must be collected within the last dose date +10, inclusive, in order to be used as LOCF. Where specified, LOCF_H (for subjects that have discontinued early due to hyperglycemia) or LOCF_{All} (for all subjects) may be used.

No adjustments for multiplicity will be performed. All tests of treatment effects will be conducted at a two-sided alpha level of 0.05 and/or two-sided 95% confidence interval (CI), unless otherwise stated.

Analysis Visit Windows

For all efficacy and safety assessments, analysis visits will be assigned according to the actual study day, calculated as the assessment date – first dose date for assessments prior to the first dose date and assessment date – first dose date +1 for assessments on or after the first dose date. The analysis visit windows will be defined as the halfway point between the target visit days:

Analysis Visit	Target Visit Day	Analysis Visit Window (Days)
Visit 1 (Screening)	N/A	N/A
Baseline	1	≤ 1
Visit 3 (Week 1)	8	2 – 18
Visit 4 (Week 4)	29	19 – 43
Visit 5 (Week 8)	57	44 – 60

Analysis Visit	Target Visit Day	Analysis Visit Window (Days)
Visit 6 (Week 9)	64	61 – 67
Visit 7 (Week 10)	71	68 – 74
Visit 8 (Week 11)	78	75 – 81
Visit 9 (Week 12)	85	82 – 99
Visit 10 (Week 16)	113	100 – 134
Visit 11 (Week 22)	155	135 – 169
Visit 12 (Week 26)	183	170 – 197
Visit 13 (Week 30)	211	198 to \leq last dose date + 10
Visit 14 (Week 34/Follow-up)	239	N/A

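### The fasting plasma glucose models adjust for the Day 1 reading only, although a second pre-treatment reading is scheduled; adding it as a covariate would buy a small gain in precision.

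*SAP*

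**What the plan says.** Change in FPG to Week 30 is the third secondary objective (Protocol 2.2, SAP 3.2) and a listed secondary endpoint (SAP 5.2). For its analysis, SAP 6.9.2.3 states: "The same MMRM and ANCOVA model as for body weight above will be performed for the change from baseline in FPG". The body-weight models in SAP 6.9.2.2 contain treatment, the HbA1c and BMI strata and one baseline value; the MMRM adds visit and treatment by visit.

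SAP 6.2 defines that baseline: "Baseline will be the measurement at Week 0 Day 1". An earlier pre-dose value is used only when the Day 1 value is missing. Protocol 11.2.2 likewise takes one value, the last one scheduled before the first dose.

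The visit list for screening (Protocol 9.1, Day -14 to Day -1) includes "Fasting glucose". The Visit 2 list (Protocol 9.3.1, Day 1) includes it again, and Appendix 1 marks the test at both visits. Nowhere do the documents average the two readings or enter the screening value as a covariate.

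**The concern.** A single fasting glucose is the subject's underlying level plus day-to-day variation. A covariate measured with that noise adjusts only partly for the underlying level, and what it misses stays in the residual variance of the treatment comparison. A second reading, taken shortly before and also untreated, would sharpen the adjustment without any new data.

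The documents support treating the two readings as similar. Metformin must be stable for at least 3 months, and Protocol 3.2 says this is to limit glucose drift before entry. Lifestyle counseling starts at Visit 2 (Protocol 7.6). Eligibility limits HbA1c but not FPG, so selection does not directly truncate the Visit 1 value.

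What is at stake is the width of the confidence interval on one secondary endpoint. FPG has no stated power, and SAP 8.2 reports more early discontinuations than expected, so precision is already lower than planned.

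**Working it through.** **1. The plan's own figure.** Only HbA1c is sized. SAP 6.1 claims power of 90% or more with 48 active and 27 placebo subjects, for a difference of 0.8 percentage points, SD 1.0 and two-sided alpha 0.05.
- Standard error = 1.0 × √(1/48 + 1/27) = 0.2406, and 0.8/0.2406 = 3.33.
- Power = Φ(3.33 − 1.96) = 91.4% by the normal formula and 90.7% by the t test, so the statement reproduces.
- The t test gives 90.2% at 46 + 27 = 73, which agrees with SAP 8.1.
- None of this concerns FPG.

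**2. Inputs for FPG (all assumed, in mg/dL).** Between-subject SD of the true level sT = 40; day-to-day SD se = 15, 20 or 25; SD of true change sd = 30. Let b be the slope of true change on true baseline level: 0 (unrelated), −0.3 or −0.5.

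**3. Formula, without the strata.** The variance of the true level left after one reading is sT²se²/(sT² + se²). After two readings, replace se² by se²/2. The residual variance at Week 30 is (1 + b)² × that quantity + sd² + se².

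Example with se = 20 and b = 0:
- One reading: 1600 × 400/2000 = 320, and 320 + 900 + 400 = 1620.
- Two readings: 1600 × 200/1800 = 177.8, and 177.8 + 1300 = 1477.8.
- Ratio: 1477.8/1620 = 0.912.

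| se | b = 0 | b = −0.3 | b = −0.5 |
|---|---|---|---|
| 15 | 0.930 | 0.963 | 0.980 |
| 20 | 0.912 | 0.952 | 0.974 |
| 25 | 0.905 | 0.947 | 0.971 |

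These ratios are too favorable. They omit the HbA1c stratum, which is already in the FPG model and carries part of the same information, and they ignore the degree of freedom spent.

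**4. Simulation with the planned terms.** ANCOVA, 70/40 randomized, 27% missing at Week 30, HbA1c and BMI strata in the model, assumed correlation 0.6 between true glucose and the variable behind the HbA1c stratum. Adding Visit 1 as a second covariate cuts the variance of the treatment difference by:
- about 5 to 7% at b = 0
- about 2 to 5% at b = −0.3
- about 1% or less at b = −0.5

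An approximate MMRM check on complete data gave 7 to 8% at b = 0 and 1 to 4% at b = −0.3. A wholly uninformative Visit 1 value raises the variance by under 2%.

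**5. Second route, through correlations.** Let r be the correlation of each reading with Week 30 and rb the correlation between the two readings. One reading leaves 1 − r²; two leave 1 − 2r²/(1 + rb).
- r = 0.5, rb = 0.8: 0.722/0.750 = 0.963.
- r = 0.3, rb = 0.9: 0.995.
- r = 0.6, rb = 0.8: 0.938.

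For readings closer to each other than to Week 30 (rb above r), this is again a gain of about 0.5 to 7%.

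**6. Covariate or average?** Suppose Visit 1 predicts Week 30 only through Day 1, for example with correlations 0.4 (Visit 1) and 0.5 (Day 1) with Week 30, and 0.8 between them. Two covariates then give a ratio of 1.000, so there is no gain, while averaging gives 1.033, a small loss. A second covariate is the safer form.

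**7. In subjects.** SAP 6.1 aims for 88 completers, and 27% missing leaves 110 × 0.73 ≈ 80. The gain is then worth 0.01 × 80 ≈ 1 to 0.07 × 88 ≈ 6 subjects.

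**The case against.** The strongest reply is that nothing in the plan is wrong. Adjusting for one pre-dose value is conventional and unbiased, and protocol and SAP agree on it. FPG has no power target, and there is no multiplicity scheme in which a little more precision would change a planned decision. All of this stands, and it is why the point is minor.

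The size also rests on inputs that the documents do not supply, and the gain can be zero. That stands too. In addition, consent is signed at Visit 1 before any study activity (Protocol 9.1). Protocol 6.10 requires fasting before visits with fasting labs, but the documents do not say how this is secured before consent. A poorer Visit 1 reading would bring the result nearer to no gain.

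A reader might go further than the documents allow in three ways:
- **That the FPG analysis is biased or discards data.** It is not biased, and the earlier reading is already the fallback baseline in SAP 6.2.
- **That every subject has two readings.** This is true by schedule only; SAP 6.2 provides for a missing Day 1 value.
- **That the gain is 7 to 10%, or up to 11 subjects of 110.** That takes the b = 0 column of the formula, which leaves out the HbA1c stratum, and applies it to all randomized subjects, although fewer will contribute Week 30 data.

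**Conclusion.** The point holds as an optional refinement of low priority. The planned FPG analysis is valid, and the HbA1c primary analysis and sample size are untouched. Under the stated assumptions the variance of the FPG treatment difference would fall by roughly 1 to 7%. The upper end needs true change to be unrelated to baseline level; the gain nearly vanishes if change depends strongly on it. The MMRM is the lead model for FPG, and the evidence for it is an approximate check on complete data only.

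**What to change.** In SAP 6.9.2.3, before database lock and unblinding, add Visit 1 fasting glucose as a second covariate in the FPG MMRM and ANCOVA. Keep change measured from the Day 1 baseline as SAP 6.2 defines it, so that the endpoint does not move. Do not average the two readings. For the few subjects with one reading missing, state a simple rule that ignores treatment, such as using the available reading for both covariates.

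The cost is one term and one degree of freedom in each model (under 2% of variance at worst), plus a baseline adjustment for FPG that differs slightly from that for HbA1c and weight. No new data are needed. Protocol 11.2.1 allows an analysis change of this kind to be made and justified in the SAP without a protocol amendment.

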6.11 Safety Analysis

All safety analyses will be conducted on the Safety Population. The evaluation of safety will be based primarily on discontinuation due to hyperglycemia, TEAEs, vital signs, safety laboratory measures, and 12-lead ECG. Other safety data will be summarized as appropriate.

6.11.1 Adverse Events

An AE is any untoward medical occurrence in a patient or clinical investigation subject administered a pharmaceutical product and which does not necessarily have a causal relationship with this treatment. All AEs, including SAEs, occurring after the subject signs the informed consent form (ICF) through the subject's final visit will be reported and monitored. All AEs will be coded using MedDRA version 20.1.

TEAEs are defined as events that are newly reported after first dose of study drug or reported to worsen in severity or relationship to study drug after first dose of study drug.

An overview of AEs will be provided by treatment group and in total for the following information:

- All TEAEs,
- Maximum severity of TEAEs,
- Study drug-related TEAEs (defined as related or possibly related),
- Maximum severity of drug-related TEAEs,
- All serious adverse events (SAEs),
- All treatment-emergent SAEs,

- Drug-related SAEs,
- Death due to AEs,
- Withdrawals due to AEs, and
- Withdrawals due to study drug-related AEs.

The numbers and percentages of subjects with TEAEs, including number of events, will be tabulated for each treatment group and in total by MedDRA system organ class and preferred term. Similar summaries will be provided by maximum severity. Drug-related TEAEs will be summarized in the same manner.

Listings of SAEs and AEs leading to study medication discontinuation will be provided.

Hyperglycemia

The number and percent of subjects permanently discontinued from the study due to hyperglycemia will be tabulated by treatment group for the Safety Population. The discontinuation rates will be compared among the treatment groups using a Fisher's exact test. The odds ratio will be provided.

AEs of Special Interest

The number and percent of subjects (including number of events) experiencing AESIs (GI events, major CV events, hypoglycemia, injection site reactions, hypersensitivity reactions and pancreatic events) will be tabulated for each treatment group and in total by category and preferred term. A listing will be provided of all AEs of special interest. For hypoglycemia, listings will be provided of all additional information such as glucose values, symptoms, countermeasures, etc. For injection site reactions, listings will be provided of all additional information such as symptoms, severity of each symptom, etc.

If data allows, the monthly hypoglycemia rate will be calculated as the event rate per subject year divided by 12 months:

$$(365.25 \times \text{total number of hypoglycemia TEAEs} / \text{study duration}) \div 12$$

Where study duration is the date of completion/early termination – date of first dose +1. Summary statistics for the monthly hypoglycemia rate will be provided by treatment group.

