## **6 STUDY TREATMENT(S)**

### **6.1 Randomization**

Subjects who meet all eligibility criteria will be randomized to treatment at visit 2 (day 1) via the Interactive Response Technology system (IRT). Randomization will be stratified using the following variables: screening HbA1c (<8.5%, ≥8.5%) and baseline BMI (<30, ≥30 kg/m^2). The randomization to the treatment arms will be 1.75:1 for the active and placebo groups, respectively. Following randomization, study drug will be dispensed in a double-blinded manner.

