### **11.2.3 Subject Disposition**

Frequencies and percentages of all randomized, discontinued, and completed subjects in the study will be presented for each of the treatment groups. A summary of discontinuations will be presented by treatment group and by visit. The reasons for discontinuations will be summarized by treatment group. Discontinuation rates will be compared among the treatment groups for each reason using a Fisher's exact test.

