### 11.3.3 Other Outcome Analyses

CCI

The proportion of subjects who discontinued due to hyperglycemia in each group will be analyzed using a logistic regression analysis with fixed effects of treatment and strata.

In addition to change from baseline in weight, CCI   
 will be listed and summarized.

CCI

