4.2 Randomization and Treatments

Subjects who meet all eligibility criteria will be randomized to treatment at visit 2 (day 1) via the Interactive Response Technology system (IRT). Randomization will be stratified using the following variables: screening HbA1c ($<8.5\%$, $\geq 8.5\%$) and baseline body mass index (BMI) (<30 , ≥ 30 kg/m²). The randomization to the treatment arms will be 1.75:1 for the active and placebo groups, respectively. Following randomization, study drug will be dispensed in a double-blinded manner. OPK-88003 and matching placebo are provided in single-use 2 mL glass vials with blue flipoff lid, an aluminum seal and a rubber stopper (septum).

This trial will evaluate 20 mg and 40 mg dose escalation and 70 mg target dose of OPK-88003 QW over a 30-week treatment period. Treatment allocation will be assigned by the IRT. The group randomized to OPK-88003 will initially receive 20 mg QW for four weeks, followed by 40 mg QW for four weeks. Once eight weeks of dose escalation are complete, subjects will receive a target dose of 70 mg QW OPK-88003 for 22 weeks. The control group will receive matched placebo SC injections QW for 30 weeks.

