6.4 Subject Disposition

Frequencies and percentages of all randomized, discontinued, and completed subjects in the study will be presented by treatment group and total. The reasons for discontinuations will be summarized by treatment group. Discontinuation rates will be compared between the treatment groups for each reason using a Fisher's exact test.

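### SAP 6.11.1 compares discontinuation for hyperglycemia with an unstratified Fisher's exact test and no stated confidence interval, and does not list this departure from the protocol's strata-adjusted analysis

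*SAP*

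**What the plan says.** Protocol 6.1 stratifies randomization by "screening HbA1c (<8.5%, ≥8.5%) and baseline BMI", and SAP 4.2 repeats this.

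Protocol 11.3.3 says that the proportion discontinued for hyperglycemia in each group "will be analyzed using a logistic regression analysis with fixed effects of treatment and strata". It does not say whether strata means HbA1c, BMI or both.

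SAP 6.11.1 says of the same event: "The number and percent of subjects permanently discontinued from the study due to hyperglycemia will be tabulated by treatment group for the Safety Population". It continues: "The discontinuation rates will be compared among the treatment groups using a Fisher's exact test", and then "The odds ratio will be provided". It names no stratum and no confidence interval. By contrast, SAP 6.9.2.1 and 6.9.2.2 name 95% Wald intervals for their odds ratios.

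Both documents also plan Fisher's test for disposition. Protocol 11.2.3: "Discontinuation rates will be compared among the treatment groups for each reason using a Fisher's exact test". SAP 6.4: "Discontinuation rates will be compared between the treatment groups for each reason using a Fisher's exact test".

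SAP section 8 covers the sample size, the move from ANCOVA to MMRM and the narrower use of LOCF. It does not mention this outcome's test. Protocol 11.2.1 asks that changes of method be described, with their justification, in the SAP or the clinical study report.

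**The concern.** The outcome is a named objective (Protocol 2.3, SAP 3.3) and an endpoint in SAP 5.4. SAP 6.11 puts it first among the measures on which the safety evaluation mainly rests. The protocol gave it an adjusted analysis of its own, separate from the disposition table. In the readable SAP the adjusted analysis is gone, and what remains largely repeats the disposition test.

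Three things are at stake, all modest:
- The estimate no longer uses a factor by which subjects were randomized. The SAP does keep the HbA1c strata for body weight and, by reference, for fasting plasma glucose.
- An odds ratio from a handful of events, without an interval, says little about precision.
- A reader of SAP section 8 would not learn that the analysis had changed.

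**Working it through.** **1. The plan's own figure.** Neither document gives an event rate or a power for this outcome. The only power statement concerns HbA1c: 48 v 27 subjects, difference 0.8, SD 1.0, two-sided 0.05. SE = sqrt(1/48 + 1/27) = 0.2406; 0.8/0.2406 = 3.326; 3.326 - 1.960 = 1.366, so power is 91.4% (90.7% with the t distribution). The stated minimum of 90% reproduces, but it says nothing about discontinuation for hyperglycemia.

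**2. Fisher with few events.** Take 70 v 40 subjects (Protocol 11.1) and assume that all are dosed. With 0 v 3 events, p = C(40,3)/C(110,3) = 9,880/215,820 = 0.046. The opposite extreme, 3 v 0, has probability 0.254 and is not added. So Fisher reaches significance with three placebo events and none on OPK-88003. In that table the logistic treatment estimate is infinite and the Wald test fails.

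**3. Fisher against the protocol's logistic model.** 8,000 simulated trials per scenario. Assumed, not in the documents: 40% of subjects with HbA1c >=8.5%, 25% with BMI <30, HbA1c-stratum odds ratio 1 to 10.

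| True rates, active v placebo | Fisher power | Wald logistic power |
|---|---|---|
| 0% v 10% | 78-79% | 0% |
| 2% v 10% | 38% | 19-21% |
| 3% v 20% | 80-82% | 69-74% |
| 5% v 25% | 84-85% | 82-87% |

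A likelihood ratio test from the same model has more power than Fisher, but its type I error is 6.3-8.2%.

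**4. Fisher against an exact test stratified by HbA1c.** Within stratum h, given the total events m_h, the active-arm count x_h is hypergeometric. Under a common odds ratio of 1,

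P(S = s) = sum over x_1 + x_2 = s of the product over h of C(a_h, x_h) C(b_h, m_h - x_h) / C(a_h + b_h, m_h),

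where a_h and b_h are the active and placebo numbers. The two-sided p-value adds all probabilities no larger than the observed one. Power and size come from full enumeration of binomial outcomes, not from simulation. The high-stratum sizes are 24/14, 28/16 and 35/20 (about 35%, 40% and 50% of subjects), with the remainder of 70/40 in the low stratum. All rates are assumed, and ranges run over the three stratum mixes.

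| Placebo v active risk (high/low stratum) | Fisher | Stratified exact | Gain in points |
|---|---|---|---|
| 30%/3% v 6%/0.5% | 48.8-62.9% | 48.9-63.2% | 0.1-0.2 |
| 40%/3% v 8%/0.5% | 62.5-78.3% | 62.9-79.3% | 0.4-1.0 |
| 50%/5% v 15%/2% | 57.1-73.8% | 58.7-77.0% | 1.6-3.5 |
| 15%/3% v 3%/0.5% | 28.4-34.9% | 28.4-34.9% | 0.0 |
| 20%/5% v 6%/2% | 24.5-31.5% | 24.5-31.5% | 0.0 |
| Null, 30%/3% in both arms | 2.2-2.5% | 3.4-3.5% | size |
| Null, 50%/5% in both arms | 1.5-1.7% | 3.5-3.7% | size |
| Null, 15%/3% in both arms | 2.7-2.8% | 2.9-3.3% | size |
| Null, 10%/10% in both arms | 3.2% | 3.2% | size |

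The stratified test stays below 5% and loses no material power in any row. Its advantage appears only when risks are high and differ strongly between strata.

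**The case against.** The strongest reply is that the SAP's choice is sensible. Fisher's test is valid with sparse or empty cells, whereas the protocol's logistic model can fail to give an estimate. Step 3 bears this out: with about 10 or fewer expected events Fisher has more power than the Wald test, and only at about 11 to 14 events are the two close. Fisher is also not new here, since the protocol already planned it for each reason for discontinuation. This stands, and it rules out a return to Wald logistic regression as the remedy.

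It does not account for the missing interval, or for the loss of the separate adjusted analysis that Protocol 11.3.3 set beside the disposition test. An exact stratified analysis keeps Fisher's robustness and restores the adjustment.

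Two further replies also stand. Text between SAP 6.9.2.3 and 6.11 is redacted, and the event is listed under Other Endpoints in SAP 5.4, so an adjusted analysis may exist there. And Protocol 11.2.1 accepts a description in the clinical study report, so silence in SAP section 8 is a gap in that list and not yet a breach.

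**Conclusion.** The point holds in a limited form. On the readable text, a planned strata-adjusted analysis has become an unstratified one without a stated interval, and SAP section 8 does not say so. Adding stratification by HbA1c is worth about 0 to 3.5 points of power. It brings the true size closer to 5% where risks differ strongly between strata. These figures rest on assumed event rates and stratum mixes, on 70 v 40 dosed subjects and on allocation balanced within HbA1c strata.

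A reader might infer more than this, and the documents do not support it:
- **That Fisher gives up power for nothing.** It does not: it handles sparse and zero cells where the protocol's model fails, and the exact alternative gains little.
- **That nearly all events come from the HbA1c >=8.5% stratum.** The glucose thresholds in Protocol Table 1 make a link plausible, but no event rate by stratum is given.
- **That the adjusted analysis has certainly been removed.** The redaction prevents that conclusion.

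This is a low-priority improvement to a safety outcome. It does not affect the primary or secondary results.

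**What to change.** 1. In SAP 6.11.1, report the exact conditional test and exact 95% CI for the common odds ratio, stratified by the randomized HbA1c stratum, for example PROC FREQ with EXACT COMOR. State the two-sided rule, because a p-value that orders outcomes by probability need not agree with the interval.
2. Keep the unstratified Fisher test in the SAP 6.4 disposition table.
3. In SAP 8.2, list and justify the change from Protocol 11.3.3, including the choice of HbA1c alone. Adding BMI would make four strata and thinner cells.
4. If the redacted text already holds an adjusted analysis, add a cross-reference in SAP 6.11.1 instead.

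The cost is a sentence or two and a few lines of code, with no new data. The analysis has limits: a stratum without events contributes nothing, and the interval is one-sided in effect when an arm has no events.

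Stratification also does not address subjects who leave early for other reasons and are counted as free of the event. A log-rank test stratified by HbA1c could be added as supportive, but it assumes that those exits are uninformative. That is doubtful given the higher than expected early dropout reported in SAP 8.2, so it should stay optional.

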3.3 Other Objectives

Other objectives of this study are as follows:

CCI

3. Percent (%) of subjects permanently discontinued from the study due to hyperglycemia;
4. Incidence and rate of gastrointestinal (GI) events, major cardiovascular (CV) events, hypoglycemia, injection site reactions, hypersensitivity reactions and pancreatic events;
5. To evaluate immunogenicity of OPK-88003 (a separate ADA report will be provided);

CCI

[figure not shown]

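### The monthly hypoglycemia rate reads as one rate per subject averaged by arm, which overweights short follow-up; the other adverse events of special interest get no time-based rate

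*SAP*

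**What the plan says.** SAP 6.11.1 plans, if the data permit, a monthly hypoglycemia rate: "the monthly hypoglycemia rate will be calculated as the event rate per subject year divided by 12 months". The formula is 365.25 times the "total number of hypoglycemia TEAEs", divided by study duration, divided by 12. For the denominator, "study duration is the date of completion/early termination" minus the first-dose date, plus 1. It then states: "Summary statistics for the monthly hypoglycemia rate will be provided by treatment group". SAP 6.2 explains what such summaries contain: "Descriptive statistics (n, mean, standard deviation, median, minimum, and maximum) will be used to summarize the continuous efficacy and safety data by treatment group".

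On the wider objective, item 4 of SAP 3.3 (and of Protocol 2.3) reads "Incidence and rate of gastrointestinal (GI) events, major cardiovascular (CV) events" and goes on to hypoglycemia, injection site reactions, hypersensitivity reactions and pancreatic events. For these categories SAP 6.11.1 plans subject counts, percentages and event counts, which "will be tabulated for each treatment group and in total by category and preferred term". SAP 5.5 lists only the number and percent of subjects. Hypoglycemia is the only category with a time denominator.

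**The concern.** Study duration is one subject's interval, and nothing in the formula sums it over subjects. A pooled arm rate is a single number with no SD, median or range, so a promise of summary statistics fits only a set of individual rates. An unweighted mean of those rates gives a subject followed for a week the same weight as one followed for eight months, although the first subject's rate is far noisier.

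This trial is exposed to that problem, because SAP 8.2 reports more early discontinuation than expected, concentrated early in the study. The median is unlikely to help. Protocol 1.3 reports no hypoglycemia-promoting effect in earlier studies, so most subjects may well have no event and the median would then be zero. The mean would be the figure that gets read.

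Two related gaps follow. The end of study duration is not pinned down: for a completer it could be Week 30 or Week 34, and for an early terminator it could be the ET visit or the later follow-up visit requested in Protocol 5.2. Also, five of the six special-interest categories have event counts but no time denominator, although the objective names a rate alongside incidence.

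**Working it through.** The documents give no hypoglycemia count, rate or exit day, so there is no figure of theirs to reproduce. The check applies the SAP formula to single subjects and then to an arm.

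**Inputs**
- Formula (SAP 6.11.1): r = (365.25 × events / days) / 12 = 30.4375 × events / days.
- Completer duration (SAP 6.2 target days): 239 days if completion is Visit 14, or 211 days if it is Visit 13.
- Early leaver's duration: not given. Assumed range is day 7 to day 57.
- If the leaver's clock runs to the follow-up visit four weeks after the final dose (Protocol 5.2; Appendix 1, note a), a one-dose subject has 28 + 1 = 29 days.
- Arm for illustration: 70 randomized to active and 56 completing (Protocol 11.1), so 14 leavers, or 20%.

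**Step 1: single-subject rates.** One event in a completer gives 30.4375/239 = 0.127 per month, or 30.4375/211 = 0.144. In an unweighted mean, the weight of a leaver's event relative to a completer's event is completer days divided by leaver days.

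| Leaver's duration (days) | Rate with one event (per month) | Weight vs 239-day completer | Weight vs 211-day completer |
|---|---|---|---|
| 7 | 4.35 | 34.1 | 30.1 |
| 14 | 2.17 | 17.1 | 15.1 |
| 29 | 1.05 | 8.2 | 7.3 |
| 57 | 0.53 | 4.2 | 3.7 |

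**Step 2: effect on an arm summary.** Take 56 completers at 239 days and 14 leavers at day 7. Total time is 56 × 239 + 14 × 7 = 13,482 days.
- One event, in a day-7 leaver: the mean of rates is 4.348/70 = 0.0621 per month; the pooled rate is 30.4375/13,482 = 0.0023.
- Thirty-four events, one in each of 34 completers: the mean of rates is 34 × 0.1274/70 = 0.0619; the pooled rate is 34 × 30.4375/13,482 = 0.0768.

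In this extreme case the mean cannot tell 1 event from 34, while the pooled rates differ 34-fold.

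**Step 3: precision when nothing is biased.** With a constant event rate and follow-up unrelated to events, both summaries are unbiased. The variance of the mean of rates relative to the pooled rate is T × Σ(1/dᵢ) / n², where T is total days, dᵢ is subject i's days and n = 70.
- Exit at day 7: 13,482 × (56/239 + 14/7) / 4,900 = 6.15.
- Exit at day 29: T = 13,790, ratio 2.02.
- Exit at day 57: T = 14,182, ratio 1.39.

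**The case against.** The strongest reply is that the averaging is inferred. The SAP speaks of a total number of events and a rate per subject-year, and never says that individual rates are averaged. That is fair, but a pooled rate does not fit the promised summary statistics, and if pooling was meant the text still has to say so.

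Several stronger readings are tempting, and the documents do not support them.

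- **That an early leaver's event counts 34-fold in general.** This needs exit on day 7, a clock that stops there, and a completer's clock that runs to Week 34. The documents give no exit day, and the SAP leaves the end date open.
- **That off-drug follow-up dilutes completers' rates by 28/211, about 13%.** SAP 6.11.1 collects adverse events through the final visit, and its TEAE definition has no post-treatment cut-off. Follow-up events can therefore enter the numerator alongside follow-up days.
- **That the result is necessarily distorted.** Under a constant rate with unrelated dropout it is only less precise, and the median and range shown beside it do not share the mean's weighting problem.
- **That the AESI objective goes unanswered.** Event counts are tabulated, SAP 6.8 summarizes exposure, and Protocol 11.4.2 plans hypoglycemia incidence between visits and AESI statistics by visit. The SAP also uses the word rate for discontinuation proportions. What is missing is the time denominator. Because the objective sets rate beside incidence, and the SAP itself treats the hypoglycemia rate as time-based, adding it is reasonable.
- **That every category needs a count model.** Protocol 11.4.1 allows for too few CV and pancreatic events even to summarize, and Protocol 1.3 describes GI events falling to near control levels by the fourth weekly dose, so a constant-rate model would fit them poorly. A plain descriptive figure is enough.

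It also stands that this is one conditional, descriptive table.

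**Conclusion.** The point holds in a limited form. On the natural reading, the arm mean of the monthly hypoglycemia rate overweights short follow-up by a factor of about 4 to 34 per event (exit at day 57 to day 7, 239-day completer). The factor is at most about 8 if early terminators are followed to the visit four weeks after the last dose. With 20% dropout and no bias, the cost is a variance 1.39 to 6.15 times that of the pooled rate, or about 2 times when each leaver has 29 days.

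Bias comes in if events cluster early or lead to exit. The documents report more early dropout than expected but give no event timing or split by arm, so bias is a risk and has not been shown. The exit days and the single-day exit pattern are assumptions. Primary and secondary efficacy results are not touched. The change is worth making because it alters the reported safety figure and is cheap.

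**What to change.** In SAP 6.11.1:

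1. Define the monthly hypoglycemia rate per arm as 30.4375 × (hypoglycemia TEAEs summed over subjects) / (study days summed over subjects), with a 95% CI. Use an exact Poisson interval if events are few. If counts allow, use a negative binomial or robust Poisson model with log time as offset and report the rate ratio.
2. State which date ends study duration for completers and for early terminators (the EOT/ET visit or the follow-up visit), and count events and time over that same window. The 10-day allowance in SAP 6.2 should not be borrowed as a cut-off. It serves the LOCF rule and the Week 30 window, and applying it to time alone would put events and time on different windows.
3. Add the same descriptive events-per-subject-time figure for the other AESI categories in SAP 3.3, item 4. No model is needed.

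The dates and event counts are already collected. The cost is a few sentences in the SAP and minor programming.
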